## V. DESIGN

This is a randomized, placebo-controlled, cross-over, single-center trial. Study drug is Botulinum toxin type A (BOTOX®). Subjects who meet the inclusion criteria for the study will be randomized to either the treatment or placebo arm.

**ARM 1 - Treatment:** Injection solution will consist of 100 units of BOTOX® in 10 cc of preservative free normal saline, or

**ARM 2 - Placebo:** Injection solution will consist of 10 cc preservative free normal saline.

The Week 16 Visit will be the end of the study participation for those subjects in Arm 1 and who did not develop ED (as defined as a drop in IIEF scores of more than 4 points from Baseline IIEF score). The Week 16 Visit will be the end of study participation for subjects in Arm 2 and who developed ED. For subjects in Arm 2, crossover to BOTOX treatment will begin after the Week 16 Visit by repeating the study schedule as for Week 0 to Week 16. Continuation visits at Months 6, 9, and 12 will occur for subjects in Arm 1 and who developed ED.

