## VII. SCHEDULE OF EVENTS

PROCEDURE	Baseline (Pre-treatment)	Week 0 Clinic Visit	Week 2 Phone Visit	Week 4 Clinic Visit	Week 6 Phone Visit	Week 8 Clinic Visit	Week 10 Phone Visit	Week 12 Clinic Visit	Week 14 Phone Visit	 Week 16 Clinic Visit (  End of Study) (  Placebo Crossover)	 Month 6 Clinic Visit	 Month 9 Clinic Visit	 Month 12 Clinic Visit (End of Study)
Signed, written informed consent	X												
Medical history	X												
Physical examination	X									X	X	X	X
Blood pressure, pulse, O 2 saturation	X									X			
Penile injection: Caverject 20mcg/cc	X									X			
Penile curvature assessment & photos	X									X			
Penile ultrasound	X									X			
IIEF questionnaire	X									X			
Randomization	X												
Penile injection: BTX-A or  Placebo		X		X		X		X					
Collect AE information		X	X	X	X	X	X	X	X	X	X	X	X
Concomitant meds	X	X		X		X		X		X	X	X	X

End of study for subjects receiving BOTOX and did not develop ED (as defined as a drop in IIEF scores of more than 4 points from Baseline IIEF score).

End of study participation for subjects receiving placebo and develop ED.

For subjects receiving placebo, crossover to BOTOX treatment will begin by repeating the study schedule as for Week 0 to Week 16.

Continuation visits for subjects receiving BOTOX and developed ED.

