Subjects randomized to ARM 2 will receive one injection of 10cc preservative normal saline at Weeks 0, 4, 8 and 12.

All subjects will be telephoned two weeks after each injection to inquire on the occurrence of any adverse events. Subjects will be asked a general, non-direct question such as, "How have you been feeling since the last visit?" Direct questioning will then be done as appropriate.

At the completion of 16 weeks (4 weeks after last treatment), subjects will have a repeat penile injection of Caverject, penile pictures will be taken, and penile ultrasonography will be performed. Subjects will also be asked to complete the IIEF again.

The Week 16 Visit will be the end of the study participation for those subjects in Arm 1 and who did not develop ED (as defined as a drop in IIEF scores of more than 4 points from Baseline IIEF score). Subjects developing ED, will have continuation visits at Months 6, 9, and 12. At these visits, a complete physical will be done. Information about any adverse events and changes in concomitant medications will be collected. The subjects will complete the IIEF questionnaire.

If at the end of 16 weeks there is a significant improvement in the subjects treated with BTX-A as compared to the placebo arm, the men in the placebo arm will be given the option to cross over into the treatment arm and complete a 12 week course of BTX-A injections (1 saline injection, 1 Botox injection, 2 saline injections). For those in Arm 2 who develop ED, participation will end after the Week 16 visit.

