Hypertension was reported in about 2% of patients. Headaches and dizziness were reported in 2% or less of patients. About 1% of the patients complained of backache. Upper respiratory infections were reported in 4% and flu-like symptoms in 2%. Sinusitis was reported in 2% and nasal congestion and coughs in 1%. Prostatic disorders were reported in 2%. Localized pain at injection site was reported in about 2% and trauma, such as, injuries, fractures, abrasions, lacerations, and dislocations were reported in 2%.

Less than 1% of patients in clinical studies reported the following events that were judged as possibly related to the use of Caverject: testicular pain and disorder, scrotal disorder, scrotal edema, hematuria, impaired urination, urinary frequency, urinary urgency, pelvic pain, hypotension, vasodilation, peripheral vascular disorder, supraventricular extrasystoles, vasovagal reaction, hypesthesia, non-generalized weakness, diaphoresis, rash, non-application site pruritus, skin neoplasm, nausea, dry mouth, increased serum creatinine, leg cramps, and mydriasis.

LIDOCAINE®: Adverse experiences with Lidocaine are, in general, dose-related and may result form high plasma levels caused by excessive dosage, rapid absorption or inadvertent intravascular injection, or may result from a hypersensitivity, idiosyncrasy or diminished tolerance on the part of the patient.

Central nervous system symptoms that may be experienced are lightheadedness, nervenousness, apprehension, euphoria, confusion, dizziness, drowsiness, tinnitus, blurred or double vision, vomiting, sensations of heat, cold or numbness, twitching, tremors, convulsions, unconsciousness, respiratory depression and arrest.

Cardiovascular manifestations are usually depressant and are characterized by bradycardia, hypotension, and cardiovascular collapse, which may lead to cardiac arrest.

Allergic reactions are characterized by cutaneous lesions, urticaria, edema, or anaphylactoid reactions. These reactions to Lidocaine are extremely rare.

The effect of the study treatments on the ability to have erections and to have intercourse is unknown. It is not known whether the treatments the subject receives in this study will worsen or will improve his ability to have intercourse

Additional risks that may be experience by subjects participating in this study are:

The risk of developing erectile dysfunction after these injections is unknown.

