## **XI. SAMPLE SIZE**

This will be a pilot study and therefore 10 subjects in each arm, for a total of 20 subjects, will allow us to determine if the therapy is effective. To allow for screen failures, 45 subjects are planned for screening.

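### The protocol gives two rules for placebo crossover to BTX-A (automatic after Week 16, or optional and only if BTX-A is significantly better) and does not say which applies

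*Combined protocol and SAP*

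**What the plan says.** Three places describe what happens to placebo men after Week 16.

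- Section V (Design): "For subjects in Arm 2, crossover to BOTOX treatment will begin after the Week 16 Visit", by repeating the Week 0 to Week 16 schedule.
- Section VII (Schedule of Events), footnote 3: "For subjects receiving placebo, crossover to BOTOX treatment will begin by repeating the study schedule as for Week 0 to Week 16".
- Section VIII (Procedures): "If at the end of 16 weeks there is a significant improvement in the subjects treated with BTX-A as compared to the placebo arm", then "the men in the placebo arm will be given the option to cross over into the treatment arm".

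All three share one exception. In section VIII it reads "For those in Arm 2 who develop ED, participation will end after the Week 16 visit"; section V and footnote 2 of section VII say the same. ED is defined as an IIEF fall of more than 4 points from baseline.

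Section XI plans "10 subjects in each arm, for a total of 20 subjects". Section XII makes change in penile curvature the primary outcome, lists blood flow, plaque size and IIEF as secondary outcomes, and plans a t-test between the two groups. It states no alpha, sidedness, effect size or standard deviation. Section VIII does not say which outcome decides whether there has been a significant improvement.

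**The concern.** Sections V and VII carry no efficacy condition and offer no choice. Section VIII carries both. The two agree in practice only when the trial favours BTX-A significantly and every eligible placebo man accepts. Otherwise staff working from the visit schedule would start BTX-A in placebo men, while staff working from Procedures would not.

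At stake is whether up to half the trial's men are exposed, after the comparison has closed, to a drug that the trial has not shown to work. The risk matters because section IX says of ED: "The risk of developing erectile dysfunction after these injections is unknown". The section VIII condition is also a comparison of groups. It cannot be evaluated until both arms have Week 16 data, whereas section V can be read as letting each man cross over after his own visit.

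**Working it through.** **Side by side**

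| Question | Sections V and VII (footnote 3) | Section VIII |
|---|---|---|
| Efficacy condition | None stated | Significant improvement over placebo at 16 weeks |
| Subject's choice | Not stated | Optional |
| Data needed first | The man's own Week 16 visit | Week 16 data from both arms |
| Arm 2 men with ED | Stop at Week 16 | Stop at Week 16 |

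The first three rows differ, and no section sets an order of precedence.

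**Plan's own figure.** Section XI: 10 + 10 = 20. Nothing more can be reproduced, because no power inputs are given.

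**How often the two rules differ.** From the plan: n = 10 per arm, two-sample t-test, df = 10 + 10 − 2 = 18. Assumed: two-sided alpha 0.05 (0.10 as a range), one deciding outcome, everyone evaluable. With standardised difference d, the noncentrality is d × √(n/2) = d × √5, and the condition is met with probability P(t > 2.101), or P(t > 1.734) at 0.10.

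| d | Met, alpha 0.05 | Rules differ, alpha 0.05 | Met, alpha 0.10 |
|---|---|---|---|
| 0 | 0.025 | 0.975 | 0.050 |
| 0.5 | 0.184 | 0.816 | 0.285 |
| 0.8 | 0.395 | 0.605 | 0.530 |
| 1.0 | 0.562 | 0.438 | 0.694 |

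**Men exposed if BTX-A has no effect**, if all accept and none is excluded for ED:

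- Sections V and VII: up to 10.
- Section VIII, one deciding outcome: 10 × 0.025 = 0.25 expected (10 × 0.05 = 0.5 at two-sided 0.10).
- Section VIII, any of the four section XII outcomes could trigger: 1 − 0.975⁴ = 0.096 if the tests are independent, and at most 4 × 0.025 = 0.10 whatever their correlation. That is about 1 man expected. At two-sided 0.10 it is 1 − 0.95⁴ = 0.185, at most 0.20, so up to 2 men.

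**Timing, only if section V means each man crosses over straight after his own Week 16 visit.** Section VI alternates odd numbers to Arm 1 and even numbers to Arm 2. Assume one man enters every s weeks, with no dropout. Placebo man k enters at (2k − 1)s and Arm 1 man j at 2(j − 1)s. When placebo man k starts crossover, Arm 1 man j has reached Week 16 if 2(j − 1) ≤ 2k − 1, that is, j ≤ k. So k of 10 Arm 1 results are in, and 9 of 10 placebo men start before all ten are. This does not depend on s.

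**Wait under section VIII.** The last man reaches Week 16 at 19s + 16 and the first placebo man at s + 16. The longest wait is 18s and the mean over the ten placebo men is 9s, with s = (52/12)/rate.

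| Assumed men per month | Longest wait, weeks | Mean wait, weeks |
|---|---|---|
| 2 | 39.0 | 19.5 |
| 4 | 19.5 | 9.75 |
| 8 | 9.75 | 4.875 |

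**The case against.** The best defence is that section VIII is the detailed text and the other two are summaries. Section V says after the visit, not immediately, and footnote 3 mainly says how crossover is carried out. Staff who apply the section VIII condition first would still start any crossover after Week 16 on the repeated schedule. This stands against the timing figures, which hold only on the immediate, per-subject reading. It does not remove the conflict. Section V states one restriction on Arm 2 (the ED exclusion) and leaves out the efficacy condition, and nothing makes section VIII prevail.

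The optional-versus-automatic difference is thin in practice. Sections X and XVII.B let any man withdraw, so nobody can be made to cross over. The efficacy condition is the substantive difference.

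A reader might infer four stronger things that the documents do not support:

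- That sections V and VII start crossover unconditionally. They do not: both stop Arm 2 men who develop ED.
- That section VIII would expose at most 0.25 men in expectation if there were no effect. That needs one deciding outcome, and section VIII names none.
- That the plan lacks a safety safeguard because Arm 1's ED results do not govern crossover. It is true that those results only lead to follow-up of the affected men ("Continuation visits for subjects receiving BOTOX and developed ED"). But section XIII.B has the principal investigator (PI) review all clinical and safety data regularly, section XIII.D lets the PI stop study drug, and Appendix II section 3.2.1 expects significant new findings to be given to subjects. With ten men a count would also be imprecise: 0 of 10 has an exact 95% upper limit of 31%.
- That the trial's result is compromised. The primary comparison ends at Week 16, before any crossover, and section XII plans no separate crossover analysis.

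**Conclusion.** The inconsistency is real and should be corrected. Sections V and VII would give BTX-A to up to 10 placebo men whatever the result, apart from those who developed ED; section VIII would offer it only after a significant result. At an assumed two-sided 0.05 with one deciding outcome, the instructions differ in 97.5%, 82%, 61% or 44% of trials at standardised differences of 0, 0.5, 0.8 or 1.0. Alpha, effect size, the single deciding outcome and accrual are assumptions, since the plan states none of them. The consequence is later exposure of placebo men, not bias in the primary comparison.

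**What to change.** Put one rule in section V, section VII footnote 3 and section VIII, for example:

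> Crossover is offered, as an option, only after all subjects in both arms have completed Week 16 or withdrawn and the primary outcome (change in penile curvature, t-test, two-sided alpha 0.05) significantly favours BTX-A. Arm 2 subjects who developed ED are not offered crossover.

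The alpha is the sponsor's choice, but it has to be written down. Without a named outcome and alpha, two people could still disagree on whether crossover is open.

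The cost is one amendment and no new data. Against section VIII it adds no wait. Against immediate crossover, the first placebo man waits about 39, 20 or 10 weeks at an assumed 2, 4 or 8 men per month, as section VIII already implies. After a long wait his Week 16 assessment is an old pre-crossover baseline; this matters little while no crossover analysis is planned.

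Optional and secondary: the PI could look at the by-arm Week 16 ED count before opening crossover, as part of the existing section XIII.B review. This sets no threshold, and the finding does not rest on it.

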## **IX. RISKS**

**BOTOX®:** It is expected that some participants may have some or all of the following side effects when given BOTOX®. Other side effects may occur which were not seen before. Side effects are usually temporary and manageable. However, it is possible they could cause serious disease or death. The study may include risks that are unknown at this time.

There have been rare reports of serious and/or immediate or even deadly abnormally sensitive reactions after treatment with BOTOX. These reactions include allergic reaction, skin rash, itching, swelling, and difficulty in breathing.

There have been rare reports of sudden death, sometimes associated with difficulty in swallowing or pneumonia. There have also been rare reports of heart problems (including irregular heart beats and heart attack, some resulting in death). Some of these patients were already at risk for heart disease. It is not known if BOTOX actually caused these problems.

It should not be used when infection is present at the injection site or in people known to be abnormally sensitive to BOTOX.

The following events have been observed since it has been marketed: skin rash, itching, and allergic reaction. In general, these side effects occur within the first week following injection and, while usually temporary, they may last several months. Pain, tenderness, or bruising around the injection site may also occur. Local weakness of the injected muscle(s) is expected. Weakness of nearby muscles may also occur due to spread of BOTOX.

BOTOX contains albumin, which comes from human blood. Although the blood is rigorously tested, there is an extremely remote risk for the transmission of viruses and similar infectious agents.

CAVERJECT®: Possible side effects of therapy with Caverject are penile pain after injection, usually mild to moderate in severity. A potentially serious reaction is priapism; therefore, patients should be instructed to seek medical attention if an erection last for more than 4 hours.

The injection can induce a small amount of bleeding at the site and a hematoma may form. There may be an occurrence of nodules or hard tissue in the penis, redness, and swelling.

Hypertension was reported in about 2% of patients. Headaches and dizziness were reported in 2% or less of patients. About 1% of the patients complained of backache. Upper respiratory infections were reported in 4% and flu-like symptoms in 2%. Sinusitis was reported in 2% and nasal congestion and coughs in 1%. Prostatic disorders were reported in 2%. Localized pain at injection site was reported in about 2% and trauma, such as, injuries, fractures, abrasions, lacerations, and dislocations were reported in 2%.

Less than 1% of patients in clinical studies reported the following events that were judged as possibly related to the use of Caverject: testicular pain and disorder, scrotal disorder, scrotal edema, hematuria, impaired urination, urinary frequency, urinary urgency, pelvic pain, hypotension, vasodilation, peripheral vascular disorder, supraventricular extrasystoles, vasovagal reaction, hypesthesia, non-generalized weakness, diaphoresis, rash, non-application site pruritus, skin neoplasm, nausea, dry mouth, increased serum creatinine, leg cramps, and mydriasis.

LIDOCAINE®: Adverse experiences with Lidocaine are, in general, dose-related and may result form high plasma levels caused by excessive dosage, rapid absorption or inadvertent intravascular injection, or may result from a hypersensitivity, idiosyncrasy or diminished tolerance on the part of the patient.

Central nervous system symptoms that may be experienced are lightheadedness, nervenousness, apprehension, euphoria, confusion, dizziness, drowsiness, tinnitus, blurred or double vision, vomiting, sensations of heat, cold or numbness, twitching, tremors, convulsions, unconsciousness, respiratory depression and arrest.

Cardiovascular manifestations are usually depressant and are characterized by bradycardia, hypotension, and cardiovascular collapse, which may lead to cardiac arrest.

Allergic reactions are characterized by cutaneous lesions, urticaria, edema, or anaphylactoid reactions. These reactions to Lidocaine are extremely rare.

The effect of the study treatments on the ability to have erections and to have intercourse is unknown. It is not known whether the treatments the subject receives in this study will worsen or will improve his ability to have intercourse

Additional risks that may be experience by subjects participating in this study are:

The risk of developing erectile dysfunction after these injections is unknown.

Inserting needles into the penis may be uncomfortable. Pain, tenderness, or bruising around the injection site may occur.

The ultrasound rarely results in physical discomfort but some anxiety before and during the procedure may be experienced.

Completing the questionnaire may cause some anxiety or embarrassment to the subject due to the personal nature of the questions.

The loss of confidentiality regarding research information is a possibility; although, the risk is very small.

## **X. CRITERIA FOR DISCONTINUING THE STUDY**

- A. Subjects unable to tolerate BTX-A due to side effects.
- B. Subjects can request removal from the study for any reason at any time.
- C. Subjects may be withdrawn at any time at the discretion of the investigator for safety, compliance, or other reasons.

A discontinuation occurs when an enrolled subject ceases participation in the study, regardless of the circumstances, prior to completing the protocol.

The reasons for a subject discontinuing from the study will be recorded in the Case Report Form.

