## VIII. PROCEDURES

Subjects who meet the inclusion criteria for the study will be randomized to either the treatment or placebo arm. Prior to treatment, all subjects will have a penile injection with Caverject 20mcg/cc to induce a penile erection. During the erect state, penile curvature will be assessed, pictures will be taken for later measurement of penile curvature, and ultrasound will be used to assess penile blood flow and plaque size. A penile duplex with intercavernosal injections of a vasoactive substance is part of our standard care for Peyronies disease diagnosis. Subjects will also be asked to complete the International Index of Erectile Function (IIEF) questionnaire.

Injections will be performed using our standard protocol currently used for verapamil injections, but instead we will be using 100 units of BTX-A in 10cc of preservative free normal saline, or 10cc of preservative free normal saline for placebo and plaque breakdown injections. The standard injection procedure consists of the following:

1. Subjects will be explained the risks and benefits of the procedure and will give informed consent.
2. Blood pressure, pulse, and oxygen saturation will be monitored throughout the procedure.
3. A penile block with 10cc of lidocaine without epinephrine will be given, followed by an observation period of 10 minutes to assure no immediate adverse reaction to lidocaine.
4. Approximately 20 to 30 injections with a 20 gage needle will be given directly into the penile plaque. The skin will not be punctured with each injection, but the needle will move within the plaque. Injection solution will consist of 100 units of BTX-A in 10 cc of preservative free normal saline, or 10 cc of preservative free normal saline.
5. Subjects in the placebo arm will only receive 10 cc of preservative free normal saline.
6. Subjects will be monitored for 1 hour after the procedure to ensure that their vital signs are stable and that there are no signs of penile hematoma.
7. Safety will be assessed by following the subject closely for one hour after the procedure.
8. Subjects will be given strict instructions to call and return to the clinic or the ER for any adverse side effects.

Subjects randomized to ARM 1 will receive one injection of 10 cc preservative normal saline at study start (week 0), followed by 100 U Botox in 10cc saline at visit two (week 4), then saline injections at weeks 8 and 12, thus a total of 4 injections (1 saline, 1 Botox, 2 saline).

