## **XII. DATA ANALYSIS**

- A. The primary outcome measure will be:
  - 1. change in penile curvature, as measured by a protractor from pictures taken at baseline versus the end of treatment at 16 weeks
- B. Secondary outcomes will be measured objectively and subjectively.
- C. Objective measures will be:
  - 1. improvements in penile blood flow
  - 2. reduction in penile plaque size as seen on ultrasound
- D. Subjective measures will be:

1. changes in IIEF scores

As mentioned above, these objective and subjective measurements will be performed before and after the 16 week treatment.

Data will be analyzed using a t-test to compare differences between the two groups.

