**D. Safety Monitoring:**

During the treatment phase of the study, participants will be asked about AEs at each visit. The investigators and/or the study coordinator will document all AEs. All AEs occurring during the course of the study will be collected, documented, and reported to the PI. AEs will be followed to the point of a satisfactory resolution. Study participants may have their study drug discontinued or they may be withdrawn from the study if the PI determines it is the best decision in order to protect the safety of the participant. Additional AE information is contained in Appendix II - Adverse Event Reporting.

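### Intolerance of BTX-A ends study participation, so Arm 1 men can lose the Week 16 primary outcome because of their reaction to the drug; the direction of the resulting bias is unknown

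*Combined protocol and SAP*

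**What the plan says.** Section X (Criteria for Discontinuing the Study) gives three criteria. Criterion A is "Subjects unable to tolerate BTX-A due to side effects". Criteria B and C are not tied to a drug: "Subjects can request removal from the study for any reason at any time" and "Subjects may be withdrawn at any time at the discretion of the investigator for safety, compliance, or other reasons". The section then defines the term: "A discontinuation occurs when an enrolled subject ceases participation in the study, regardless of the circumstances, prior to completing the protocol".

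Section XIII.D (Safety Monitoring) puts it differently: "Study participants may have their study drug discontinued or they may be withdrawn from the study", where the investigator judges this best for the participant's safety.

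On exposure, Section VIII (Procedures) gives Arm 1 its BTX-A at Week 4 with saline at Weeks 0, 8 and 12, "thus a total of 4 injections (1 saline, 1 Botox, 2 saline". For the other arm, "Subjects randomized to ARM 2 will receive one injection of 10cc preservative normal saline at Weeks 0, 4, 8 and 12".

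The Schedule of Events (Section VII) places the curvature assessment and photographs at Baseline and Week 16 only. Section XII makes the change between those two visits the primary outcome and says "Data will be analyzed using a t-test to compare differences between the two groups". It names no analysis population and no method for missing outcomes. Section XI plans 10 men per arm and allows for screen failures, but not for loss after randomisation.

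**The concern.** Criterion A refers to one arm's drug, and by the definition in the same section it ends follow-up as well as injections. A man who leaves before Week 16 has a baseline curvature and nothing to compare it with, because no intermediate or early-termination curvature reading is scheduled. Unless some other rule is applied, he drops out of the t-test.

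This goes beyond a missing-data plan that was never written. A stated rule links loss of the primary outcome to something that happens after randomisation and that, before Week 16, can happen only in Arm 1. The men left in Arm 1 would then be partly selected by their reaction to the treatment under test, and the comparison with Arm 2 would no longer be between the groups as assigned. With 10 men per arm, each such loss is a tenth of Arm 1.

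**Working it through.** **Step 1. Which routes out of the study reach which arm before Week 16.**

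| Route | Arm 1 | Arm 2 |
|---|---|---|
| Section X, criterion A (intolerance of BTX-A) | Yes, once BTX-A has been given | No, only saline is given |
| Section X, criterion B (own request) | Yes | Yes |
| Section X, criterion C (investigator's discretion, including safety) | Yes | Yes |

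Criterion A is an extra route that is open only to Arm 1. Under Section VIII there is no further BTX-A to stop after Week 4, so what criterion A adds from then on is departure from the study.

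**Step 2. What departure costs.** Curvature is read at two visits. Leaving before the second means no primary outcome. Section X offers no assessment after discontinuation. Section XIII.D leaves room for a man to stop drug and stay, but does not say that his Week 16 assessment is then done.

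**Step 3. Size of the bias.** The plan has no figure to reproduce: Section XI gives no effect size, SD, error rate, power or dropout rate. All inputs below except the 10 per arm are assumptions.

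- k = Arm 1 men lost under criterion A: 1 to 3 of 10. No loss in Arm 2, to isolate the effect of this criterion.
- D = mean improvement of Arm 1 completers minus that of the men lost, in SD units: 0.5 to 1.5 in absolute value, either sign.
- Two-sided 5% t-test, equal SDs, no true difference between the arms as randomised.

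The full-arm mean is (1 − k/10) × completers' mean + (k/10) × leavers' mean. Hence completers' mean − full-arm mean = (k/10) × D, which is the bias in the arm difference. It favours the drug if D > 0, works against it if D < 0, and is nil if D = 0.

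The error rate comes from the noncentral t distribution with 18 − k degrees of freedom and noncentrality (k/10) × D / √(1/(10 − k) + 1/10). For k = 2, D = 1: 0.20 / √(1/8 + 1/10) = 0.20 / 0.474 = 0.42, which gives 6.8%.

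| k | Absolute bias at \|D\| = 0.5, 1, 1.5 SD | Two-sided error at \|D\| = 0.5, 1, 1.5 SD |
|---|---|---|
| 1 | 0.05, 0.10, 0.15 | 5.1%, 5.5%, 6.1% |
| 2 | 0.10, 0.20, 0.30 | 5.5%, 6.8%, 9.1% |
| 3 | 0.15, 0.30, 0.45 | 5.9%, 8.8%, 13.7% |

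The error rates are the same for +D and −D, so they say nothing about which arm gains.

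**Step 4. Precision.** The difference detectable with 80% power (exact t) is 1.32 SD with 10 v 10, and 1.37, 1.42 and 1.48 SD after losing 1, 2 or 3 Arm 1 men.

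**Step 5. How likely losses are.** The documents give no intolerance rate. With an assumed rate p per man and 10 men in Arm 1, P(at least one lost) = 1 − (1 − p)^10:

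| p | At least 1 lost | At least 3 lost |
|---|---|---|
| 5% | 40% | 1.2% |
| 10% | 65% | 7.0% |
| 20% | 89% | 32% |

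**The case against.** A reader might infer that the rule tilts the result towards the drug, on the view that men who cannot tolerate BTX-A would have done worse. The documents do not support this. Nothing in them links intolerance to change in curvature, and if side effects went with a stronger local effect, the bias would run the other way.

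A reader might also take selective loss from Arm 1 as certain. It is not. No rate is given, criteria B and C can remove Arm 2 men too, and both arms undergo the same penile block and repeated needle passes. Arm 2 losses could offset or add to the bias. They do not cancel a route that only Arm 1 has.

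Third, it can be said that Section XIII.D already lets a man stop drug and remain. That is a fair reading, and no text gives Section X precedence. But Section XIII.D does not secure the Week 16 measurement, and a site that followed Section X would end participation. The conflict stands.

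Fourth, exclusion from the analysis is nowhere stated; it is inferred from the silence of Section XII. That is correct, and it is why the fix has to cover both sections.

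Finally, Section VI allocates by odd and even enrolment number, so the protection expected from randomisation is already weak. This is a separate weakness and no defence: staff who can work out the arm are better placed to apply criteria A and C differently.

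**Conclusion.** The point holds as a design weakness that should be corrected. Sections X and XIII.D disagree on whether intolerance ends treatment or participation. Read as written, Section X lets Arm 1 men lose their primary outcome because of their reaction to the drug, and Section XII does not say how that loss is handled. The direction of any bias is unknown.

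Its size rests wholly on assumptions. For 1 to 3 losses and a leaver–completer difference of 0.5 to 1.5 SD either way, the bias is 0.05 to 0.45 SD in absolute value and the nominal 5% error becomes 5.1% to 13.7%. The upper end needs three losses and a 1.5 SD difference together and is an extreme case; with one loss the error stays between 5.1% and 6.1%. Two losses move the detectable difference from 1.32 to 1.42 SD. Confidence is high on the wording conflict and the missing analysis rule, and much lower on how much harm would follow.

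**What to change.** - **Section X:** separate stopping study injections from leaving the study, and bring the text into line with Section XIII.D. Obtain the scheduled Week 16 curvature photograph, ultrasound and IIEF from every randomised man who stops injections, unless he withdraws consent or the assessment is judged unsafe for him. Record the reason for each outcome that is missed, by arm.
- **Section XII:** state that the primary comparison uses all randomised men in their assigned arm. Add a sensitivity analysis for outcomes still missing that varies the assumption in both directions, with missing men taken as better and as worse than completers.

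The clinical rule for stopping injections is not changed.

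The cost is protocol wording plus one already scheduled visit for the few men who stop. That visit is not trivial, because the photograph requires the Caverject injection. The safety exception may leave some men without data, which is one reason for the sensitivity analysis. The estimate will also include men who missed some study injections. Under Section VIII those after Week 4 are saline, so planned BTX-A exposure would be complete by then. Sections III, V and VII are less clear about which injections contain BTX-A and should be reconciled with Section VIII.
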